9.4.3. Other Events that Require Accelerated Reporting to Sponsor

The following events also require reporting to the sponsor (or designee) within 24 hours of learning of the event:

Symptomatic Overdose of Study Drug: Accidental or intentional overdose of at least 2 times the intended dose of study drug within the intended therapeutic window, if associated with an AE.

Pregnancy: Although pregnancy is not considered an AE, it is the responsibility of the investigator to report to the sponsor (or designee), within 24 hours of identification, any pregnancy occurring in a female patient, or female partner of a male patient, during the study or within 24 weeks of the last dose of study drug. Any complication of pregnancy affecting a female study patient, or the female partner of a male study patient, and/or fetus and/or newborn that meets the SAE criteria

must be reported as an SAE. Outcome for all pregnancies should be reported to the sponsor.

Adverse Events of Special Interest: All AESI, serious and nonserious, must be reported within 24 hours of identification using the same reporting process as for SAE reporting, per Section 9.4.2. Adverse events of special interest for this study include the following:

- Anaphylactic reactions
- Allergic reactions and/or local injection site reactions that require consultation with another physician for further evaluation
- Increase in ALT or AST: $\geq 3 \times$ ULN (if baseline $<$ ULN), or ≥ 2 times the baseline value (if baseline \geq ULN)
- Pregnancy
- Symptomatic overdose with evinacumab
- Neurocognitive events
- New onset of diabetes: The definition of new onset of diabetes will be the following:
 - Type 1 or type 2 diabetes TEAE (grouping of Medical Dictionary for Regulatory Activities [MedDRA®] terms will be specified in the SAP)and/or
 - At least 2 values of HbA1c $\geq 6.5\%$ during the TEAE period. **NOTE:** For patients with only a single measurement available during the TEAE period, a single value $\geq 6.5\%$ will be considered and qualify the patient as new onset of diabetes by default. For patients with several HbA1c measurements but only with the last one $\geq 6.5\%$, this single value $\geq 6.5\%$ will be considered and qualify the patient as new onset of diabetes by default.and/or
 - At least 2 values of fasting glucose ≥ 126 mg/dL (7.0 mmol/L). **NOTE:** For patients with only a single measurement available during the TEAE period, a single value ≥ 126 mg/dL (7.0 mmol/L) will NOT be considered and will NOT qualify the patient as new onset of diabetes. For patients with several fasting glucose measurements but only with the last one ≥ 126 mg/dL (7.0 mmol/L), this single value ≥ 126 mg/dL (7.0 mmol/L) will NOT be considered and will NOT qualify the patient as new onset of diabetes- Pancreatitis

Refer to the study manual for the procedures to be followed.

9.4.4. Reporting Adverse Events Leading to Withdrawal from the Study

All AEs that lead to a patient's withdrawal from the study must be reported to the sponsor's medical monitor within 30 days.

Refer to the study reference manual for the procedures to be followed.

9.4.5. Abnormal Laboratory, Vital Signs, or Electrocardiogram Results

The criteria for determining whether an abnormal objective test finding should be reported as an AE include:

- the test result is associated with accompanying symptoms, and/or
- the test result requires additional diagnostic testing or medical/surgical intervention, and/or
- the test result leads to a change in dosing (outside of protocol-stipulated dose adjustments), discontinuation from the study, significant additional concomitant drug treatment, or other therapy

Contact the medical monitor in the event the investigator feels that an abnormal test finding should be reported as an AE, although it does not meet any of the above criteria.

Repeating an abnormal test, in the absence of any of the above conditions, does not constitute an AE. Any abnormal test result that is determined to be an error does not require reporting as an AE.

Evaluation of severity of laboratory abnormalities will be assessed according to the scale outlined in Section 9.5.1.

9.4.6. Follow-up

Adverse event information will be collected until the patient's last study visit.

Serious adverse event information will be collected until the event is considered chronic and/or stable.

9.5. Evaluation of Severity and Causality

9.5.1. Evaluation of Severity

The severity of AEs will be graded according to the following scale:

- **Mild:** Does not interfere in a significant manner with the patient normal functioning level. It may be an annoyance. Prescription drugs are not ordinarily needed for relief of symptoms, but may be given because of personality of the patient.
- **Moderate:** Produces some impairment of functioning but is not hazardous to health. It is uncomfortable or an embarrassment. Treatment for symptom may be needed.
- **Severe:** Produces significant impairment of functioning or incapacitation and is a definite hazard to the patient's health. Treatment for symptom may be given and/or patient hospitalized.

If a laboratory value is considered an AE, its severity should be based on the degree of physiological impairment the value indicates.

Infusion Reactions

The severity of infusion reactions will be graded according to the following scale (semi-colon indicates “or” within description of the grade):

- **Mild:** Mild transient reaction; infusion interruption not indicated; intervention not indicated.
- **Moderate:** Therapy or infusion interruption indicated but responds promptly to symptomatic treatment (eg, antihistamines, NSAIDs, narcotics, IV fluids); prophylactic medications indicated for ≤ 24 hours.
- **Severe:** Prolonged (eg, not rapidly responsive to symptomatic medication and/or brief interruption of infusion); recurrence of symptoms following initial improvement; hospitalization indicated for clinical sequelae; life-threatening consequences; urgent intervention indicated; death.

9.5.2. Evaluation of Causality

Relationship of Adverse Events to Study Drug:

The relationship of AEs to study drug will be assessed by the investigator, and will be a clinical decision based on all available information. The following question will be addressed:

Is there a reasonable possibility that the AE may have been caused by the study drug?

The possible answers are:

Not Related: There is no reasonable possibility that the event may have been caused by the study drug

Related: There is a reasonable possibility that the event may have been caused by the study drug

A list of factors to consider when assessing the relationship of AEs to study drug is provided in [Appendix 2](#).

The investigator should justify the causality assessment of each SAE.

Relationship of Adverse Events to Study Conduct:

The relationship of AEs to study conduct will be assessed by the investigator, and will be a clinical decision based on all available information. The following question will be addressed:

Is there a reasonable possibility that the AE may have been caused by study conduct?

The possible answers are:

Not Related: There is no reasonable possibility that the event may have been caused by study conduct

Related: There is a reasonable possibility that the event may have been caused by study conduct

A list of factors to consider when assessing the relationship of AEs to study conduct is provided in [Appendix 2](#).

The investigator should justify the causality assessment of each SAE.

Relationship of Adverse Events to study drug infusion:

The relationship of AEs to the infusion procedure will be assessed by the investigator, and will be a clinical decision based on all available information. The following question will be addressed:

Is there a reasonable possibility that the AE may have been caused by the infusion procedure?

The possible answers are:

Not Related: There is no reasonable possibility that the event may have been caused by the infusion procedure

Related: There is a reasonable possibility that the event may have been caused by the infusion procedure

A list of factors to consider in assessing the relationship of AEs to infusion procedure is provided in [Appendix 2](#).

The sponsor will request information to justify the causality assessment of SAEs, as needed.

9.6. Safety Monitoring

The investigator will monitor the safety of study patient at his/her site(s) as per the requirements of this protocol and consistent with current Good Clinical Practice (GCP). Any questions or concerns should be discussed with the sponsor in a timely fashion. The sponsor will monitor the safety data from across all study sites. The medical monitor will have primary responsibility for the emerging safety profile of the compound, but will be supported by other departments (eg, Pharmacovigilance and Risk Management; Biostatistics and Data Management). Safety monitoring will be performed on an ongoing basis (eg, individual review of SAEs) and on a periodic cumulative aggregate basis.

9.7. Investigator Alert Notification

Regeneron (or designee) will inform all investigators participating in this clinical trial, as well as in any other clinical trial using the same investigational drug, of any SAE that meets the relevant requirements for expedited reporting (an AE that is serious, unexpected based on the Investigator's Brochure or this protocol, and has a reasonable suspected causal relationship to the medicinal/study drug).

10. STATISTICAL PLAN

This section provides the basis for the SAP for the study. The SAP may be revised during the study to accommodate amendments to the clinical study protocol and to make changes to adapt to unexpected issues in study execution and data that may affect the planned analyses. The final SAP will be issued before the database is locked.

Analysis variables are listed in Section 4.

10.1. Statistical Hypothesis

There is no formal statistical hypothesis testing planned for this trial, as the primary objective is to estimate the magnitude of treatment effect on TG lowering.

10.2. Justification of Sample Size

Percent change in TG is analyzed based on log (post/pre) transformation, allowing for a normal distribution of the data. Standard deviations (SD) of raw percent changes up to 13% are akin to moderate SD on the log scale (30-40%). For the statistical precision calculations, a log-scale SD of 0.5 was used based on available evinacumab phase 1 data, and is assumed to be conservative. With N=10 patients, the 90% confidence interval (CI) for an estimated mean reduction in triglycerides of 40% is approximately 20% to 55%. With N=12, the CI is 22% to 54%. A sample size of 24 is considered adequate to analyze the percent change in TG in the 3 genetic cohorts. Assuming a 20% drop out rate, approximately 30 patients will be needed to assess TG. Additional patients (up to a maximum of approximately 50 patients) will be enrolled with the intent to explore the effect of evinacumab on development of pancreatitis.

For the FDG-PET uptake signal SUV_{max} , prior data on steroid-treated patients yielded a natural log-scale SD of change of 0.66 ([Shigekawa 2010](#)). This yields 80% power to yield a statistically significant (alpha=0.05, 1-sided) change from baseline within the N=16 evinacumab-treated patients if the TRUE underlying geometric mean ratio (post/pre) is 0.65 (back-transformed from the log-scale; ~35% reduction). For comparison to the N=8 placebo-treated patients, assuming log-scale SD=0.15 for placebo based on reproducibility data, and 0.66 for evinacumab, there is 80% power if the TRUE underlying geometric mean ratio (GMR) of GMR's (evinacumab post/pre divided by placebo post/pre) is 0.64 (~36% reduction).

For the key MRI endpoint "mean f", which is the weighting coefficient between contrasting MRI regions ([Klauss 2015](#)) reported summary statistics which yield an SD estimate at most 5.96 for change from baseline. With this assumed SD, the N=24 patients with evinacumab post- and pre-values have 80% power to yield a statistically significant (alpha=0.05, 1-sided) change from baseline if the TRUE underlying mean change is 3.12 (~30% from baseline 10.5, which was observed by Klauss [[Klauss 2015](#)]). For the between-treatment comparison (N=16 evinacumab vs N=8 placebo), there is 80% power if the TRUE difference is 6.62 (~63% of the 10.5 baseline value observed by Klauss [[Klauss 2015](#)]).

10.3. Analysis Sets

10.3.1. Full Analysis Set

The full analysis set (FAS) includes all randomized patients who receive any randomized study drug; it is based on the treatment assigned (as randomized). Only observed data will be analyzed/summarized; no missing data will be imputed. Efficacy endpoints and baseline characteristics will be analyzed using the FAS.

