3.2. Double-Blind Safety Analysis Set

The double-blind safety analysis set (SAF) considered for safety analyses will be the randomized population who received at least 1 dose or part of a dose of double-blind study drug. Patients will be analyzed according to the treatment received (placebo or evinacumab). In addition:

- Randomized patients for whom it is unclear whether they took the study drug will be included in the safety population as randomized.
- For patients receiving study drug from more than 1 treatment group during the double-blind period, the treatment group allocation for as-treated analysis will be evinacumab.

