3.6. Patient-Reported Outcomes (PRO) Analysis Set

The analyses of the PRO data in the respective treatment period (DBTP and SBTP) will be performed on all randomized patients who received any double-blind study treatment with a baseline and at least 1 non-missing post-baseline PRO evaluation. Treatment assignments for the DBTP are based on the treatment received (placebo or evinacumab).

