3.7. PET Analysis Set

The analyses for PET will be performed on all randomized patients who received any double-blind study treatment with a baseline and a post-baseline PET evaluation. Treatment assignments are based on the treatment received (placebo or evinacumab).

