5.7.3. Analysis of Other Variables

Descriptive statistical analyses for other endpoints (described in Section 4.7.3) will be summarized by treatment group and overall for the study, as well as by treatment group and overall in the FAS population. For summary tables, only protocol scheduled measurements (as defined by e-CRF visit label) will be included. Patient listings will include all measurements, scheduled and unscheduled.

The summary of results for other variables will be presented separately for the DBTP and SBTP, unless otherwise noted. Summaries for the DBTP will be presented by treatment groups

(evinacumab, placebo) containing patients from the double-blind safety analysis set. Summaries for the SBTP will be presented by all patients and by treatment group in DBTP (i.e., evinacumab, placebo), for patients in the single-blind safety analysis set. No formal inferential testing will be performed for either period. Summaries will be descriptive in nature.

Hs-CRP and HbA1c parameters will be summarized at each protocol-scheduled visit. The medians (with Q1-Q3) will be plotted for hs-CRP and HbA1c. Applying the PCSV criteria at any time during the TEAE period, the number of patients (and percentages) meeting the criteria will be summarized.

Similar tables, except PCSV criteria, will be provided for post heparin LPL activity, APOC2, APOA5, and metabolic parameters.

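### The SAP assigns PRO, PET and MRI arms by treatment received although the protocol puts efficacy endpoints on the as-randomised FAS; the change is not listed, and SAP 5.7.3 names two populations

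*Protocol*

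**What the plan says.** Protocol 10.3.1 says of the FAS that "it is based on the treatment assigned (as randomized", and then: "Efficacy endpoints and baseline characteristics will be analyzed using the FAS". Protocol 10.3.2 uses treatment received for compliance and clinical safety.

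The SAP departs from this in four places:

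- **3.6 (PRO):** "Treatment assignments for the DBTP are based on the treatment received (placebo or evinacumab". Section 3.8 (MRI) has the same sentence.
- **3.7 (PET):** "Treatment assignments are based on the treatment received (placebo or evinacumab".
- **5.7.3 (HbA1c, hs-CRP, post-heparin LPL activity, apolipoproteins, metabolic parameters):** results are first to be "summarized by treatment group and overall for the study, as well as by treatment group and overall in the FAS population". The next paragraph describes double-blind summaries by arm "containing patients from the double-blind safety analysis set". SAP 3.2 groups that set by treatment received.

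For a patient given drug from both arms, SAP 3.2 adds that "the treatment group allocation for as-treated analysis will be evinacumab". That rule appears under the double-blind safety set only.

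SAP 3.1 keeps the FAS as randomised. The primary triglyceride (TG) analysis (5.7.1), the main lipid summaries (5.7.2) and the biomarkers (5.12) use it. SAP 1.2.4 lists six modifications of the protocol. Item 3 splits the safety set by period. Item 5 refers to 5.7.2 and 5.9 to 5.12 and concerns methods. None mentions a change in how arms are assigned.

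**The concern.** PET, MRI and the section 5.7.3 variables are efficacy variables by SAP 4.7. The questionnaires stand under the efficacy heading of the Schedule of Events, and patient-reported symptoms are a protocol secondary endpoint. The protocol's as-randomised rule therefore covers all of them.

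These endpoints also carry the trial's between-arm contrasts outside TG. Protocol 10.4.3.2 compares evinacumab with placebo on PET, with MRI handled similarly. SAP 5.11 calculates a double-blind PRO difference with a 95% confidence interval. If a patient receives the wrong product, grouping by treatment received lets the dosing error decide the comparison group. The same patient could then be placebo in the FAS lipid or biomarker tables and evinacumab in the PRO, PET or MRI tables. Section 5.7.3 cannot be programmed without someone choosing between its two populations.

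**Working it through.** **Text comparison (double-blind period)**

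| Variables | Protocol 10.3.1 | SAP |
|---|---|---|
| Primary TG | FAS, as randomised | FAS, as randomised (5.7.1) |
| Lipids, main summaries; biomarkers | same | FAS, as randomised (5.7.2, 5.12) |
| PRO, PET, MRI | same | treatment received (3.6, 3.7, 3.8) |
| Other variables | same | FAS and as-treated safety set (5.7.3) |

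Rows 3 and 4 do not match the protocol, and none of the six items in SAP 1.2.4 covers them.

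**The plan's own figures.** Inputs are from Protocol 10.2: 16 evinacumab and 8 placebo patients, one-sided alpha 0.05.

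- PET: log-scale SDs 0.66 and 0.15, ratio of geometric mean ratios 0.64. SE = √(0.66²/16 + 0.15²/8) = 0.1733; |ln 0.64|/SE = 0.4463/0.1733 = 2.575. The noncentral t with 22 df gives 80.2% power (Welch, 17.9 df: 79.7%). The stated 80% reproduces.
- MRI: difference 6.62, SD 5.96. 6.62/(5.96·√(1/16 + 1/8)) = 2.565, giving 80.0% with 22 df. The stated 80% reproduces.

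**How far the two bases can diverge.** The documents give no misdosing rate, so the number of errors is assumed. Let D = ln 0.64, and let k of the 8 placebo patients receive a fraction f of the evinacumab effect and be counted as evinacumab in the as-treated grouping.

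- As randomised: D·(1 − kf/8)
- As treated: D·(16 + kf)/(16 + k)

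| Scenario | As randomised | As treated | As-treated arms |
|---|---|---|---|
| No error | 0.640 | 0.640 | 16 vs 8 |
| 1 placebo patient, evinacumab throughout (f = 1) | 0.677 | 0.640 | 17 vs 7 |
| 2 such patients | 0.716 | 0.640 | 18 vs 6 |
| 1 placebo patient, one infusion (f = 1/3 assumed) | 0.652 | 0.651 | 17 vs 7 |
| 1 evinacumab patient, placebo throughout: D·15/16 | 0.658 | 0.640 | 15 vs 9 |

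One patient is 1/8 = 12.5% of the placebo arm used in these calculations. At 50 enrolled, about 50/3 ≈ 17 are on placebo, so one patient is 1/17 = 5.9%. One full error there gives 0.64^(16/17) = 0.657 as randomised against 0.640, if all 17 have both scans.

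The table shows divergence, not bias. The as-treated column returns 0.640 after a full swap because the illustration assumes that misdosing is unrelated to the patient's own course. Randomisation does not guarantee that.

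**The case against.** The best case against acting is that the two groupings coincide unless a patient gets the wrong product. Both the FAS and the double-blind safety set contain randomised patients who received double-blind drug. Doses are given in clinic (Protocol 7.7.4) from numbered blinded supplies (7.7.1). Protocol 10.1 plans no formal hypothesis test. SAP 5.7.4 and 5.7.5 summarise PET and MRI descriptively and test only within the evinacumab group, and SAP 5.11 rules out formal testing of PRO. The new analysis sets are announced at the start of SAP section 3, so nothing is hidden.

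All of this stands, and it limits the size of the point. It does not remove it. The SAP itself expects that some patients may not be treated as randomised: 3.2 has a mixed-dosing rule, and 4.5 and 5.5 require listings of such patients. A descriptive difference with a confidence interval is still read as a randomised comparison. No reason is given for leaving the protocol's rule.

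Three stronger readings are tempting, and the documents do not support them:

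- **That the randomised comparisons are broken.** They are exposed only if misdosing occurs.
- **That SAP 5.7.3 moves the other variables to treatment received.** It names both populations, so the defect is a contradiction.
- **That a placebo patient given one evinacumab infusion would be moved to evinacumab for PRO, PET and MRI.** SAP 3.2 states that rule for the safety set alone, and 3.6 to 3.8 neither repeat nor cite it. Those sets have no stated rule for mixed dosing, which is a gap of its own. Even if the rule were applied, the single-infusion scenario gives almost the same ratio either way.

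**Conclusion.** The point holds as an unlisted departure from the protocol for PRO, PET and MRI, plus an internal contradiction in SAP 5.7.3. Its effect on results is nil without misdosing. With misdosing it depends on the number and extent of errors: on the protocol's 16 versus 8 and its assumed PET effect, from about 0.001 on the ratio for one single-infusion error to 0.037 for one placebo patient fully misdosed and 0.076 for two. These figures rest on assumed errors and, for the single infusion, on an assumed one third of the effect.

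The primary TG result is not at risk. It is a within-patient change on the FAS, pooled over both groups and aligned to the start of evinacumab.

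A reader might also infer that lipids stay on the as-randomised FAS throughout. They do not: SAP 5.7.2 uses the single-blind safety set for that period and the double-blind safety set for the optional summary combining both periods. An edit confined to 3.6 to 3.8 and 5.7.3 would therefore still leave two rules for lipids. The point merits correction because the change is cheap and the SAP's purpose is to settle such choices before unblinding.

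**What to change.** SAP wording only:

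1. In 3.6, 3.7 and 3.8, assign double-blind arms as randomised, and keep the existing baseline and post-baseline data requirements. This also removes the need for a mixed-dosing rule in those sets.
2. In 5.7.3, name the FAS as the single population for double-blind summaries and delete the reference to the double-blind safety set.
3. In 5.7.2, base the combined double-blind and single-blind lipid summary on the FAS.
4. Keep treatment received for safety, PK and ADA. It may be added as a sensitivity analysis for efficacy.
5. If the sponsor prefers treatment received for any efficacy variable, list it in 1.2.4 with the reason, and state how mixed dosing is handled in that set.

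There is no cost in patients, visits or data collection. SAP section 1 allows revision on blinded data, with the final plan issued before the first interim database lock; the edit belongs in that window.
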